#### **6.1.3 Method of Assignment/Randomization**

Participants will be randomized to order of menthol conditions and WS-3 or WS-23 conditions.

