In the main study session, participants will engage in a 15-min training session of the psychophysical tasks they will use to report sensory experience at Lab 1. For Labs 1-3, participants will engage in six directed puffing bouts (5 puffs/3 sec puffs/30 second interpuff intervals) will be separated by 30 mins to allow any sensory effects to dissipate between exposures, a procedure adapted from [name] previous studies. Puffing will occur using a puff topography device (i.e., an established device in which the e-cigarette is attached to a mouthpiece) to measure the parameters of each puff taken (puff duration, volume, etc.). During the 15-minute training session at Lab 1, participants will familiarize themselves with vaping using a puff topography device. Following bout, participants will complete in the following order measures of overall liking/disliking, intensities of sweetness, bitterness, cooling, and irritation/harshness, and where irritation/harshness is felt (i.e., mouth, throat, both). Sensory measures will be followed by collection of general appeal and reinforcing efficacy measures, and a post-exposure measure of craving (collected 15-min after exposure). Cardiovascular measures, including blood pressure and heart rate, will be recorded both before and after each bout session. Participants will be randomized to receive one of the 3 menthol conditions (no-menthol, low menthol, high menthol, levels determined by the pilot study above) in Lab 1 and will receive the alternative conditions in randomized order in Lab 2 and Lab 3. During each lab session the menthol condition will be paired with three WS-3 concentrations: no WS-3, low WS-3, or high WS-3 and three WS-23 concentrations: low WS-23, high WS-23, or 4% WS-23 (concentration determined by pilot study) in randomized order. E-cig pods containing e-liquids will be weighed before and after the session. Lab sessions will occur no more frequently than every 24-hrs. At the end of

each of the three lab sessions, participants will choose between the 6 e-liquids they sampled in the lab using a free-choice paradigm.

**Debrief:** Following study completion, participants will be thanked for their participation and will be given information from the CDC on cigarette smoking and e-cigarette cessation.

**Table 4.** List of Study Assessments

	Pre-screening	Intake (pilot)	Lab 1 (Pilot)	Intake (main)	Lab 1 (main)	Lab 2 (main)	Lab 3 (main)
Contact Info & Eligibility Review	X						
Informed Consent		X		X			

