### **6.4 Statistical Method**

#### **6.4.1 Statistical Design**

Preliminary analyses will provide an overview of the data (e.g., randomization success, outcome distribution, missingness patterns). Outcome analyses will be intent-to-treat and use mixed-effects models which allow for different numbers of observations/subject, use all available data, and can handle missing-at-random data. If model assumptions will appear to be violated, we will transform the data or fit more flexible generalized linear or nonparametric mixed models. For the pilot study, separate mixed-effects models will examine the influence of different concentrations of menthol, WS-23 and WS-3 on coolness and overall intensity and will be used to select the concentrations of menthol and WS-3 that product the weak but detectable coolness and the maximum coolness. For the main study, separate mixed-effects model will include menthol (0, Concentration 1, Concentration 2), WS-3 (0, Concentration 1, Concentration 2), WS-23 (0, Concentration 1, Concentration 2, Concentration 3) and time within lab as factors, all interactions among those factors and adjust for stratification variables. A combination of random effects and structured variance-covariance matrices will be used to account for within-subject correlations. The best-fitting structure will be selected based on Akaike information criterion (AIC). For the main study, higher liking/wanting for WS-3 (at Concentration 1 or 2) or WS-23 (at Concentration 1 or 2 or 3) combined with menthol (at Concentration 1 or 2), compared to menthol alone, will be supportive of the primary hypothesis. Similar models will examine the other outcomes and interactions of different concentration combinations of WS-3, WS-23 and menthol with nicotine. Exploratory analyses will also consider the impact of sex, combustible tobacco use and nicotine dependence on experiences from WS-3, menthol and nicotine.

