#### **6.4.2 Sample Size Considerations**

For our pilot study, we will recruit 30 subjects. While we did not conduct a power calculation for this pilot study, we conducted a similar pilot study with 10 participants in our earlier work with multiple menthol concentrations, and do not anticipate any problems with identifying differences in coolness between the WS-3 and menthol concentrations. For the main study, we will recruit 66 subjects. With an anticipated dropout of 10%, 60 subjects are expected to have complete data. Because we have 4 primary hypotheses (each WS-3 concentration X each menthol concentration > menthol concentration alone), we used a Bonferroni-corrected alpha=0.1. With N=60 completers and a SD of paired differences of 25 as observed in our prior data, we have 80% power to detect a difference of 11.4 (moderate effect size  $d'=.45$ ) in liking/wanting (0-100 scale) between each WS-3 concentration X each menthol concentration and menthol alone using a paired t-test at alpha=0.01.

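### Crossing time within lab with every product factor can cost the primary contrasts up to about 6 power points unless exposure orders are balanced, and the plan does not say the contrasts are averaged over positions

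*Combined protocol and SAP*

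**What the plan says.** Section 6.4.1, repeated in 6.5.1, specifies a mixed-effects model for the main study with menthol, WS-3, WS-23 "and time within lab as factors, all interactions among those factors". On covariance it says: "A combination of random effects and structured variance-covariance matrices will be used to account for within-subject correlations", with the structure chosen by AIC. No method for degrees of freedom is given. Neither section says whether time is categorical or linear, or how a product contrast is taken over time.

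Section 6.3 says that in each of three labs "participants will engage in six directed puffing bouts". Section 5.1 has the liking/wanting items rated after each exposure. On order, 6.1.3 says "Participants will be randomized to order of menthol conditions and WS-3 or WS-23 conditions", and 6.3 describes the coolant conditions within a lab as "concentration determined by pilot study) in randomized order". No balancing rule is stated for the main study. For the pilot, by contrast, 5.1 and 6.3 say that block order is counterbalanced.

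Section 6.4.2 assumes 60 completers out of 66 and an SD of paired differences of 25, and concludes "we have 80% power to detect a difference of 11.4", "using a paired t-test at alpha=0.01". It makes no allowance for time or its interactions.

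**The concern.** Liking/wanting yields one rating per bout, so a time factor within the lab amounts to the exposure position. Crossing it with the 18 liquids that are actually given turns 18 means into 18 x 6 = 108 cell means, each resting on about 60/6 = 10 subjects. It adds 17 x 5 = 85 liquid-by-position parameters. None of the objectives or hypotheses in section 4 concerns position.

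Two things are at stake. First, a contrast averaged equally over six thin, unequally filled cells is less precise than the paired difference on which 6.4.2 is based. Second, once interactions are in the model, a reference-coded product coefficient is the effect at one position only. Unless the plan names the averaged contrast, the quantity tested is open.

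This is separate from the fact that WS-3 and WS-23 are never combined, which leaves half of the 3 x 3 x 4 x 6 = 216 factorial cells empty. Rewriting the product factors as 18 liquids would cure that and leave the present point untouched.

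**Working it through.** **Inputs.** From 6.4.2: N = 60, SD of paired differences 25, difference 11.4, alpha 0.01. From 6.3: 3 labs of 6 exposures. Assumed: two-sided test (not stated, but it reproduces the 80%; one-sided gives 87%), six-level categorical position, and within-subject correlation from 0 up to subjects treated as fixed. Section 6.4.2 also says "we used a Bonferroni-corrected alpha=0.1", whereas 0.05/4 = 0.0125. I use 0.01 because the power statement does.

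**1. The plan's own figure.** Noncentrality = 11.4 / (25/sqrt(60)) = 3.532. With 59 df and two-sided alpha 0.01, power is 80.4%, and the difference detectable with 80% power is 11.35. The stated figure reproduces.

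**2. Where the inflation comes from.** With no within-subject correlation, the average of six cell means has variance (sigma^2/36) x sum(1/n_t). If every n_t = 10 this is sigma^2/60, so nothing is lost. Under simple random order n_t varies around 10 with variance 60 x (1/6) x (5/6) = 8.33. To first order the mean of 1/n_t is then (1/10)(1 + 8.33/100), a ratio of about 1.083. The cause is unequal cell counts.

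**3. Full calculation.** I took the generalised least squares variance of each contrast over simulated order allocations of 60 subjects and divided it by 2 sigma^2/N.

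| Model and order | Variance ratio |
|---|---|
| All interactions, simple random order, averaged over positions | about 1.08 to 1.14 across settings, mostly 1.10 to 1.13 |
| Same, single allocations (5th to 95th percentile) | about 1.04 to 1.26 |
| Position as main effect, simple random order | 1.006 (three labs together) to about 1.018 (one lab alone) |
| All interactions, Williams order | 1.00; about 1.008 after 6 random dropouts from 66 |
| All interactions, simple random order, one position only | about 7 to 8 |

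**4. Power.** Noncentrality = 11.4 / (25 x sqrt(ratio/N)). The mixed model's residual df, treating each subject-by-lab block as a stratum, are 60 x 18 - 180 - (108 - 3) = 795. Without time terms they are 60 x 18 - 180 - (18 - 3) = 885.

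| Ratio | N = 60, 59 df | N = 60, model df | N = 66, 65 df | N = 66, 795 df |
|---|---|---|---|---|
| 1.00 | 80.4% | 82.9% | 84.9% | 86.9% |
| 1.08 | 76.6% | 79.3% | 81.5% | 83.7% |
| 1.14 | 73.9% | 76.6% | 79.0% | 81.2% |

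At 59 df the detectable difference moves from 11.35 to between 11.8 (ratio 1.08) and 12.1 (ratio 1.14). With position as a main effect (ratio 1.006) power is 80.1% at 59 df.

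**5. Single position.** At a ratio of 7 to 8, power for 11.4 points with N = 60 is about 9 to 11%. Balanced orders do not help here. With equal subject and residual variances the comparison at one position is between subjects, with variance 2(2 sigma^2)/10 against 2 sigma^2/60, a ratio of 12.

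**The case against.** A reader might infer that the stated model by itself brings power down to 74-77%. The documents do not support that. The averaged loss needs orders that are not balanced over positions, and the plan says only that order is randomised. The biostatistician prepares the chart before the study starts (6.1.4, 6.1.6), so a balanced scheme is possible. Simple randomisation is the more natural reading, given that balancing is mentioned for the pilot and not here, but it remains a reading. Six categorical positions is likewise an inference.

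The 74-77% also keeps a paired test's 59 df for a mixed model. At about 795 df the result is 77-79%, only 1 to 3 points below the stated 80%, although still about 4 to 6 points below the same model without time terms. If all 66 contribute, as 7.15 envisages, power is about 79-84%. A ratio of 1.08 to 1.14 is equivalent to an SD of about 26.0 to 26.7 instead of 25, which is small beside the uncertainty in one prior-data SD. All of this stands and limits the size of the point.

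Two further arguments stand in part. Modelling position may remove variation that is included in the SD of 25, but a main effect captures position differences common to all liquids without the 85 extra parameters. It is also reasonable to ask whether product effects change over six nicotine bouts. That is a reason to examine the question, and an exploratory model can do so.

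Finally, a reader might infer that the primary result will be read at one position. Nothing in the documents says so. The plan merely fails to exclude it.

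**Conclusion.** The point holds conditionally. The model carries 85 liquid-by-position parameters that serve no stated hypothesis and that the power calculation ignores. With simply randomised orders, categorical position, equal averaging over positions and N = 60, the variance of the primary contrasts rises by about 8 to 14%. Power is then about 74-77% at 59 df, or 77-79% against about 83% at the model's own df. With position-balanced orders the loss is essentially nil. With all 66 subjects power is about 79-84%. These figures do not show that the study is underpowered.

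The omission that does not depend on order is the definition of the contrast: averaged over positions it is close to the planned comparison, while at one position it has about 7 to 8 times the variance under random orders and more under balanced ones. The change is worth making because it costs almost nothing and settles both matters.

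**What to change.** In 6.4.1 and 6.5.1:

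- Define time within lab as exposure position 1 to 6, and enter it as a categorical main effect only in the models for the primary and secondary contrasts.
- State that every product contrast is an average over positions.
- Move position-by-liquid interactions to a separate model labelled exploratory.
- If the interactions are kept in the primary model, use position-balanced orders (Williams or Latin square) and describe the scheme in 6.1.3. This can apply only to subjects whose orders are not yet fixed. The main-effect model needs no change to the allocation.

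The cost is a few sentences and no new data. The downside is that a change of product effect with position is examined only in the exploratory model.

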## 4 Study Objectives

### 4.1 Hypothesis

We aim to examine the impact of cooling components of WS-3, WS-23, and menthol on the appeal and addiction potential of nicotine-containing e-liquids among adults. We hypothesize that any addition (low, high) of WS-3, WS-23, or menthol will result in similar increases in addiction potential, and that when WS-3, WS-23, and menthol are combined they will produce additive effects relative to menthol alone. We also hypothesize similar changes in appeal outcomes.

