### 4.2 Primary Objective

Examine addiction potential (liking/wanting) and appeal (overall flavor appeal, intensity, sweetness, bitterness, irritation, cooling), following a single exposure (5 puffs) to nicotine-containing e-cigs (~59 mg/ml nicotine salt, commonly used in commercial e-cigs), with one of three WS-3 concentrations (none, low, high) and one of the three WS-23 concentrations (low, high, 4%) in combination with one of three menthol concentrations (none, low, high).

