### **6.5 Planned Analyses**

#### **6.5.1 Primary, Secondary, and Exploratory Objective Analysis**

For the pilot study, separate mixed-effects models will examine the influence of 5 different concentrations of menthol and WS-3 on coolness and overall intensity and will be used to select the concentrations of menthol and WS-3 that product the weak but detectable coolness and the maximum coolness. For the main study, separate mixed-effects model will include menthol (0, Concentration 1, Concentration 2), WS-3 (0, Concentration 1, Concentration 2), WS-23 (0, Concentration 1, Concentration 2, Concentration 3), and time within lab as factors, all interactions among those factors and adjust for stratification

variables. A combination of random effects and structured variance-covariance matrices will be used to account for within-subject correlations. The best-fitting structure will be selected based on Akaike information criterion (AIC). For the main study, higher liking/wanting for WS-3 (at Concentrations 1 or 2) or WS-23 (at Concentrations 1 or 2 or 3) combined with menthol (at Concentration 1 or 2), compared to menthol alone, will be supportive of the primary hypothesis. Similar models will examine the other outcomes and interactions of different concentration combinations of WS-3/WS-23 and menthol with nicotine. Exploratory analyses will also consider the impact of sex, combustible tobacco use and nicotine dependence on experiences from WS-3/WS-23, menthol and nicotine.

Oral microbiome and inflammatory marker assessment will serve as another exploratory objective in this study. Microbial testing, including DNA extraction, library preparation and sequencing methods, will be performed at the CosmosID lab. The analysis will evaluate alpha and beta diversity across different flavor-use groups, with the significance of group-wise clustering determined using a permutational multivariate analysis of variance (MANOVA). Statistical methods such as ANOVA, t-tests and chi-square will assess between-group differences, while controlling for nicotine concentration based on total nicotine equivalents measured in urine samples from participants.

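### The decision sentence lets any of ten WS-3 or WS-23 comparisons support the primary hypothesis, while the sample-size section counts, adjusts and powers only the four WS-3 ones and prints two different alphas

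*Combined protocol and SAP*

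**What the plan says.** **Hypothesis (4.1).** It makes two predictions. The first concerns each constituent added by itself: "any addition (low, high) of WS-3, WS-23, or menthol will result in similar increases in addiction potential". The second, in the same sentence of the protocol, concerns mixtures of the constituents: "when WS-3, WS-23, and menthol are combined they will produce additive effects relative to menthol alone".

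**Primary objective (4.2).** WS-23 is included on the same footing as WS-3: "one of the three WS-23 concentrations (low, high, 4%) in combination with one of three menthol concentrations (none, low, high". In Table 2 (section 5.1), WS-23 fills 9 of the 18 cells.

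**Decision sentence (6.4.1, repeated in 6.5.1).** Support for the primary hypothesis is defined as "higher liking/wanting for WS-3 (at Concentration 1 or 2) or WS-23 (at Concentration 1 or 2 or 3) combined with menthol" at either non-zero concentration, against menthol alone. Section 6.5.1 has the same wording: "or WS-23 (at Concentrations 1 or 2 or 3) combined with menthol (at Concentration 1 or 2), compared to menthol alone". Neither section says how many comparisons must succeed, and neither gives a multiplicity rule.

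**Sample size (6.4.2).** The section counts "4 primary hypotheses (each WS-3 concentration X each menthol concentration > menthol concentration alone". For the significance level it says "we used a Bonferroni-corrected alpha=0.1". It then states 80% power for 11.4 points with 60 completers and an SD of paired differences of 25, "using a paired t-test at alpha=0.01". The main-study calculation does not mention WS-23.

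**Interactions.** The planned model contains all interactions among the factors, and interactive effects are the secondary objective (4.3). No contrast is named for them.

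**The concern.** The three places that should define the primary claim define it differently. From the documents alone one cannot say whether the primary family has four members or ten, at what alpha each is tested, or whether a WS-23 result on its own would support the hypothesis. The only adjustment appears in the sample-size section, so it is not confirmed as an analysis rule even for the four comparisons it covers.

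Two things are at stake. First, one positive cell for one coolant could be presented as support for a hypothesis about all of them, and choosing the family after unblinding would be data-driven. Second, the stated power belongs to the four-comparison family, not to the rule in 6.4.1 and 6.5.1.

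A smaller point concerns wording. The decision sentence tests whether a combination exceeds menthol alone. That does not show that effects add up in the strict sense, or that the three constituents have similar effects.

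**Working it through.** **Inputs.** From 6.4.2: 60 completers, SD of paired differences 25, difference 11.4, power 80%, printed alphas 0.1 and 0.01. Assumed because not stated: two-sided tests and, for corrected alphas, an overall level of 0.05.

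**Step 1: count the comparisons.**
- Decision sentence: (2 WS-3 + 3 WS-23) × 2 menthol = 10.
- Sample-size section: 2 WS-3 × 2 menthol = 4.
- Hypothesis 4.1 read literally (low and high only, so without 4% WS-23): (2 + 2) × 2 = 8.

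**Step 2: reproduce the stated power.** For a paired t-test, df = 59 and the noncentrality is 11.4 / 25 × √60 = 3.53. Power comes from the noncentral t distribution.

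| Two-sided alpha | Where it comes from | Power for 11.4 | Difference at 80% power |
|---|---|---|---|
| 0.1 | printed in 6.4.2 | 96.8% | 8.1 |
| 0.0125 | 0.05/4 | 82.7% | 11.1 |
| 0.01 | printed in 6.4.2 | 80.4% | 11.35 |
| 0.00625 | 0.05/8 | 75.3% | 11.9 |
| 0.005 | 0.05/10 | 72.8% | 12.2 |

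The plan's figure therefore rests on two-sided 0.01. The printed 0.1 does not fit it, and neither printed value equals 0.05/4.

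**Step 3: size of the error inflation at 0.01.** This is a null simulation with 40,000 replicates, 60 participants, equal and independent errors per condition, and the menthol-alone cell shared by its five combinations.
- Ten comparisons, at least one significantly higher: about 4%.
- Ten comparisons, at least one significant in either direction: about 8% (Bonferroni bound 10 × 0.01 = 10%).
- The four WS-3 comparisons, at least one significantly higher: about 2%.

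**Step 4: what superiority over menthol alone does not show.** Strict additivity concerns the four-cell contrast: combination − menthol alone − same coolant without menthol + neither. Take invented effects relative to neither: menthol +10, coolant +20, combination +21.4. The combination beats menthol alone by 21.4 − 10 = 11.4, yet the contrast is 21.4 − 10 − 20 = −8.6, which is less than additive.

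**Step 5: which differences the SD of 25 covers.** Menthol level is fixed within a lab session (5.1, 6.1.2), so combination versus the same menthol level alone is a within-session difference. Coolant without menthol versus menthol without coolant always compares two sessions. Its SD may exceed 25, and the documents give no figure for it.

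**The case against.** The strongest reply has four parts.

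1. **The 0.1 is a misprint.** This is very likely right: the next sentence uses 0.01, and only 0.01 reproduces the 11.4 points. A reader might infer that the trial will test at 0.1 and inflate error heavily. The documents do not support that. The slip should be corrected, but correcting it still leaves four against ten.

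2. **Ten comparisons at 0.01 do little harm.** This also stands. A false higher result somewhere has a chance of about 4%, so this is not a large loss of error control.

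3. **Additive and similar can be read loosely.** Section 4.1 names menthol alone as the comparator for additivity, and the decision sentence uses that comparator. Similar need not mean formal equivalence. A reader might infer that the plan promised strict additivity and equivalence tests and then left them out; the text does not go that far. What remains is an ambiguity in how results may be described.

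4. **The model contains every interaction.** True, so the information will be there. But no section ties a contrast to either statement, and the only decision rule given is superiority over menthol alone.

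Ten is also not the only defensible family. Eight follows from the wording of 4.1, and four is what 6.4.2 already powers. The documents must choose one.

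**Conclusion.** The point holds as an inconsistency in how the primary claim is defined. Sections 6.4.1 and 6.5.1 admit ten comparisons. Section 6.4.2 counts, adjusts and powers four, leaves WS-23 out, and prints an alpha of 0.1 that its own power figure contradicts. If all ten are primary at an assumed overall two-sided 0.05, power for 11.4 points at the strictest step is 73% instead of 80%, and the difference detectable with 80% power is 12.2.

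This should be settled before unblinding. It does not threaten the data or the design. The 4% and 8% error figures assume equal, independent errors per condition; the power figures take the plan's SD of 25 and 60 completers as given. Neither severe error inflation nor a broken promise of equivalence or additivity testing follows from the documents.

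**What to change.** 1. **Alpha (6.4.2).** Correct the 0.1 and state the overall level and sidedness.

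2. **One family (6.4.1, 6.4.2, 6.5.1).** Replace the sentence joined by or with a separate liking/wanting claim for each coolant level × menthol level against the same menthol level alone. Choose one of:
   - all ten under one adjustment, for example Holm at overall 0.05 (strictest step 0.005: 73% power for 11.4 points, 12.2 detectable at 80%);
   - eight, with 4% WS-23 secondary, following the low and high wording of 4.1 (0.00625: 75%, 11.9);
   - the four WS-3 comparisons, with WS-23 explicitly secondary and taken out of the decision sentence (power about as stated).

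   Restate power for the family chosen. Say that the adjustment covers liking/wanting only, because 5.2.1 also lists LHS and gLMS ratings as primary outcomes.

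3. **Additivity.** Do not claim it in the strict sense from superiority over menthol alone. Base any such statement on the four-cell contrast with its 95% CI, from the planned model under the secondary objective.

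4. **Similarity.** Do not infer it from non-significance. Report each WS-3, WS-23 and menthol level alone versus neither, and the differences among them including WS-3 versus WS-23, as estimates with 95% CIs. Note that coolant-versus-menthol differences are between sessions.

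**Cost.** Wording, plus contrasts from the model already planned; no new data. Claims become narrower and, if WS-23 stays primary, stated power falls slightly. The loss under Holm matters mainly when few effects are real: if all ten true differences were 11.4, average power per comparison would be about 86% under the same error assumptions.
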